15 STATISTICAL ANALYSIS

Descriptive data will be presented as a mean and standard deviation for continuous variables. For statistical analyses, the normality of the data distribution will be assessed by the Shapiro-Wilk test. To compare differences between groups in the studied variables, the Student's t-test will be used for normally distributed data. For each group, a paired ttest will be used to compare baseline and follow-up scores, and the 95% confidence interval (CI) will be calculated for the mean differences.

The theoretical sample size based on a 10-point difference (10%) in the DASH between the two studied groups, assuming a 95% confidence interval, 80% statistical power and 24 20% sampling error, resulted in 36 patients in each group.

25 All analyses will be conducted using SPSS Statistical Package for Windows, version 25

26 (SPSS Inc., 2009, Chicago, Illinois, USA). The significance level was set at P < 0.05.

27

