7 STUDY DESIGN

8 A pilot feasibility study, single bling with two groups (experimental and control group). 9 Clinical outcome measures will be shoulder function and pain (Constant Murley Score 10 and Disabilities of the Arm, Shoulder, and Hand or DASH score). Each variable will be 11 measured by a blinded physiotherapist at baseline and at one month follow-up. Patients 12 performed the prescribed exercises either supervised by the physiotherapist (control 13 group) or in a separate room without therapist supervision (experimental group).

14

15 **Regarding the study population**.

16 Patients who will be referred to the rehabilitation service of the University Hospital of

17 Elche (Spain) for physiotherapy treatment (manual therapy, exercise, stretching, and

18 electrotherapy) after suffering orthopedic injury or surgery in the shoulder joint complex,

19 from July 2023 to December 2023 will be considered for enrollment in the study.

20 Inclusion criteria were established as follows:

- 21 (i) be at least 18 years old and be able to read and understand Spanish.
- 22 (ii) suffer a traumatic or degenerative shoulder injury, with or without surgical
 23 treatment.
- (iii) have a prescription for rehabilitative physical therapy that includes active exercises.
- 26

27 The exclusion criteria adopted were:

Patients were excluded if they had a concomitant injury on an upper extremity or the cervical spine at the time of participation or sequelae of previous injuries in the area.

30

31 Regarding sample size

The main objective of this study is to know whether a clinical trial will be feasible and to have an estimate of standard deviation, which will be used in the sample size calculation for the large-scale trial; to estimate the rate (proportion) of eligible people who are willing to participate, of participants who drop out of the trial, or of participants who comply with the assigned intervention. That is why the sample size could be between 20 and 40 participants.

38

39 **METHODOLOGY**

40 Following baseline examination, patients will be randomly assigned to either 41 physiotherapist-supervised exercise (control group) or monitoring by the eFisioTrack

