19 OUTCOME MEASURES

The baseline measures will be collected before randomization and the outcome assessments will blind. All assessment measures, will be collected by the same clinician who was not involved in the treatment programs. In addition, at the physiotherapy service patients received a paper copy of the questionnaires to fill out on their own.

The following patient-reported outcome measures were used to assess participants' shoulder pain and function: the Disabilities of Arm, Shoulder and Hand (DASH) score and the Constant-Murley (CM) score.

27 • Primary outcome measures

The DASH was taken as a primary outcome measure. It is one of the most widely used self-reported questionnaires that measures symptoms and degree of function related to a disorder in the upper extremity. It has been validated in Spanish and comprises 30 items: 21 about physical function, 6 for symptoms, and 3 to assess social aspects. In addition, there are two optional modules, each with four items, which are used to assess symptoms and function in those whose functional demands are not included in the main part of the questionnaire.

This instrument has been used in previous studies involving physical therapy and exercise for shoulder injuries. It is scored in two components: first the symptom questions (30 items) and second the optional modules. The assigned values for all completed responses are summed and averaged, producing a score that is then transformed on a scale of 0 to 100 by subtracting one and multiplying by . A higher score indicates greater disability. Differences in scores are considered clinically relevant (minimum clinically important difference or MCID) when they are above 10 points.

42 • Secondary outcome measures

The CM score is a commonly used specific instrument for assessing the shoulder joint.
The maximum score is 100 points, 90 to 100 being excellent, 80 to 89 good, 70 to 79

1 medium, and less than 70 poor, considering that the scores can vary with age. This tool 2 includes a subjective assessment of the patient's pain and ability to perform daily 3 activities (35 points) and an objective assessment of mobility and strength by physical 4 examination (65 points). Its use has been specifically validated in shoulder arthroplasty, 5 rotator cuff repair, adhesive capsulitis, and fractures of the proximal humerus, but not in 6 shoulder instability.

7

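### The between-group DASH comparison has a planned method only if Shapiro-Wilk does not reject normality; one unconditional analysis should be named instead

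*Combined protocol and SAP*

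**What the plan says.** The Statistical Analysis section first states that continuous variables will be summarised by mean and standard deviation, without any condition. It then says that "the normality of the data distribution will be assessed by the Shapiro-Wilk test" and, for comparing the groups, that "the Student's t-test will be used for normally distributed data". No rank test, transformation, bootstrap or other method is named there or elsewhere for data judged non-normal.

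The within-group paired t-tests and their 95% confidence intervals, in the following sentence, carry no normality condition.

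The only significance level is general: "The significance level was set at P < 0.05". It is not tied to the normality check. The protocol also does not say whether the check applies to each arm or to pooled data, or to raw scores, changes or residuals.

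On the primary outcome, the Outcome Measures section says: "The DASH was taken as a primary outcome measure". It is measured at baseline and "at one month follow-up" (Study Design). The plan does not say whether follow-up scores or changes are compared between arms. The sample size paragraph of Study Design gives a pilot of 20 to 40 participants.

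**The concern.** The one randomised comparison of the primary outcome depends on a preliminary test that can fail by chance, and no method is given for when it does. The analyst would then choose between, say, a rank test, a transformation and the t-test after seeing the data. Whether the DASH effect is reported as a mean difference in points or on some other scale would depend on the sample drawn.

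The plan itself uses the mean-difference scale: it sets the clinically relevant DASH difference at 10 points and bases its theoretical sample size on that figure. Non-normal scores are plausible here. DASH is bounded at 0 and 100, and eligibility covers traumatic and degenerative injuries, with or without surgery.

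**Working it through.** **Inputs.** From the protocol: two groups; 20 to 40 participants in total; DASH as primary outcome; a significance level of 0.05; Shapiro-Wilk; Student's t-test for normal data. Assumed: equal allocation, so 10 to 20 per arm; Shapiro-Wilk run at 0.05; a baseline to follow-up correlation of 0.5 to 0.7; gamma distributions of shape 4 (moderate skew) and shape 2 (strong skew) as illustrations only. The plan gives no figure of its own for how often the check fails, and nothing below depends on its 36 per group.

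**Step 1. How often normal data fail.** With k independent tests at 0.05, the chance of at least one rejection is 1 − 0.95^k.

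- One pooled test, k = 1: 5.0%.
- One test per arm, k = 2: 1 − 0.9025 = 9.75%.
- Baseline and follow-up in both arms, k = 4: 1 − 0.8145 = 18.5%. The time points are correlated, so this is approximate; simulation at an assumed correlation of 0.5 gave 17.8% to 18.6%.

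Simulation of the one-test-per-arm reading gave 9.1% to 9.8% at 10, 15, 20 and 36 per arm. Sample size hardly matters when the data are normal.

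**Step 2. How often skewed data fail.** Simulated share of trials in which at least one arm is rejected:

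| Data | 10 per arm | 20 per arm |
|---|---|---|
| Normal | 10% | 10% |
| Gamma, shape 4 | 26% | 50% |
| Gamma, shape 2 | 42% | 78% |

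For shape 2, 100 − 42 = 58% of trials pass at 10 per arm and 100 − 78 = 22% at 20 per arm.

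**Step 3. Does the t-test need the check?** Under no true difference, with equal-sized arms of equal shape, the ungated t-test had a type I error of 4.4% to 4.9% with gamma shape 2 data at 10 and 20 per arm. Among trials that passed the check it was higher, at 6.1% to 8.0% across repeated simulations. In this setting the check removes no error that the t-test had.

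**Step 4. What baseline adjustment gains.** In large samples the ratio of the ANCOVA standard error to that of a t-test is √(1 − r²) against follow-up scores and √((1 + r)/2) against change scores. Estimating the covariate slope multiplies either by about √(1 + 1/(2n − 4)), with n per arm: √(1 + 1/16) = 1.031 at n = 10 and √(1 + 1/36) = 1.014 at n = 20.

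| n per arm | r | Against follow-up | Against change |
|---|---|---|---|
| 10 | 0.5 | 1 − 0.866 × 1.031 = 11% | 1 − 0.866 × 1.031 = 11% |
| 10 | 0.7 | 1 − 0.714 × 1.031 = 26% | 1 − 0.922 × 1.031 = 5% |
| 20 | 0.5 | 1 − 0.866 × 1.014 = 12% | 1 − 0.866 × 1.014 = 12% |
| 20 | 0.7 | 1 − 0.714 × 1.014 = 28% | 1 − 0.922 × 1.014 = 7% |

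Simulation against follow-up scores gave 10% to 26% at 10 per arm and 13% to 27% at 20. A fair summary is 10% to 27% against follow-up scores and 5% to 12% against change scores.

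The gain against follow-up scores vanishes when 1 − r² = 1/(1 + 1/(2n − 4)), that is, at r of about 0.24 for n = 10 and 0.16 for n = 20.

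**The case against.** The strongest reply is that this is only a missing fallback. With Mann-Whitney as an assumed fallback, the two-stage procedure had an overall type I error of 4.6% to 5.7% across normal and both gamma settings at 10 and 20 per arm. That stands: a reader might infer that the check inflates the trial's false-positive rate, and with a named fallback it does not do so materially. The higher error in Step 3 applies only to trials that pass. What a fallback does not cure is that the sample drawn would still decide whether the result is a mean difference or a rank comparison.

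A second reply also stands. A reader might infer that the standard deviation wanted for the large-scale trial is at risk. It is not: means and SDs are reported without condition, as are the paired analyses, and the arm means give the point difference.

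Other tempting inferences go beyond the text.

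- The 10% figure is not a property of the plan as written. It needs one test per arm at 0.05.
- The protocol does not say that raw scores rather than residuals are tested. For a per-arm check the distinction is empty, because subtracting an arm's mean does not change the Shapiro-Wilk result.
- The check is not blind to strong skew. At 20 per arm it stops 78% of the strongly skewed trials.

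Finally, it may be said that ANCOVA is a separate matter. In part it is: the gap could be closed by an unconditional t-test. But a replacement sentence is needed anyway, and the baseline scores are already available.

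**Conclusion.** The point holds in a limited form. It is certain from the text that the only planned between-group test is conditional on normality and that no alternative is named, so on rejection the primary test and its interval would be chosen after the data are seen.

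How often this would happen rests on assumptions: about 10% with normal data for one test per arm at 0.05, within a range of about 5% to 19% over other readings, and more with skew. The gamma figures illustrate that rise; they are not estimates for DASH. The finding that the t-test does not need the check is shown for equal-sized arms of equal shape at 10 to 20 per arm, and should not be carried further.

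For a pilot of this size this is a change that should be made. It does not invalidate the study.

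**What to change.** Remove the Shapiro-Wilk condition and state one primary analysis for all cases: ANCOVA of one-month DASH on arm and baseline DASH, reporting the adjusted mean difference, its 95% CI and the residual SD. Do the same for Constant-Murley. Inspect residuals graphically, without letting the plots change the primary method. Name any sensitivity analysis in advance.

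With one unconditional method, the share of trials without a planned between-group test falls to zero. At an assumed correlation of 0.5 to 0.7 there is also the gain in precision shown in Step 4; its size depends on whether the plan meant follow-up or change scores.

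The cost is a short rewrite of the analysis paragraph and standard SPSS procedures, using scores already collected before randomisation. The small statistical price is one degree of freedom for the covariate, which could cancel the gain over follow-up scores if the correlation is low.

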2 OBJECTIVES

The main aim of the study was to evaluate the effect on clinical variables of monitoring exercises prescribed for shoulder injury rehabilitation with the eFisioTrack platform in patients of the Rehabilitation Service at University Hospital of Elche.

6

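### The between-group t-test leaves the tested quantity unnamed and the pre-randomisation baseline unused; a baseline-adjusted model (ANCOVA) would be a nearly free gain

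*Combined protocol and SAP*

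**What the plan says.** The only between-group method is in the Statistical Analysis section: "To compare differences between groups in the studied variables, the Student's t-test will be used for normally distributed data". No covariate, regression model or adjustment appears anywhere in the protocol. The following sentence gives a paired t-test within each group, and the 95% CI that "will be calculated for the mean differences" belongs to that within-group comparison. It therefore does not settle what is compared between groups. The 10-point DASH difference used for sizing is also not identified as a difference in scores or in changes.

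Baseline values are available. Study Design has DASH and Constant-Murley measured at baseline and at one month, and Outcome Measures states: "The baseline measures will be collected before randomization".

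The protocol gives two main purposes. Objectives says "The main aim of the study was to evaluate the effect on clinical variables". The sample-size paragraph of Study Design says the main objective is feasibility, including an "estimate of standard deviation, which will be used in the sample size calculation" for a larger trial, and allows 20 to 40 participants.

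**The concern.** A t-test on one-month scores ignores the baseline. A t-test on changes fixes the baseline slope at 1, which loses precision unless the true slope, rho × SD(follow-up)/SD(baseline), is near 1. The two tests can give quite different answers from the same data. If neither is named in advance, the choice could be made after the data are seen.

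Two things are at stake. With at most 40 participants and a clinical effect as a stated main aim, the width of the between-group interval matters. And the pilot is meant to supply an SD for the main trial, but the follow-up SD, the change SD and the residual SD after baseline adjustment lead to different sample sizes.

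**Working it through.** **Inputs from the protocol.** Difference 10 DASH points; 80% power; significance level 0.05, taken as two-sided; theoretical size 36 per group; pilot of 20 to 40 in total.

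**Assumptions.** The SD, the correlation rho and the ratio of the SDs at the two visits are not given. Allocation is taken as 1:1 with no dropout, so 10 or 20 per group is a best case.

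**The plan's own figure.** The size "resulted in 36 patients in each group" cannot be reproduced without an SD. Using n = 2 × 7.849 × SD²/10², an SD of 15 gives 35.32, rounded up to 36. If a 20% loss is already included (36 × 0.8 = 28.8, or 36/1.2 = 30), the implied SD is about 13.4 to 13.8. If the test is one-sided, it is about 17. SD 15 is used below, with this range as a check.

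**Large-sample variance, equal SDs.** Relative to the one-month t-test, the factor is 2(1 − rho) for change and 1 − rho² for ANCOVA. ANCOVA relative to change is (1 + rho)/2.

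| rho | change / one-month | ANCOVA / one-month | ANCOVA / change |
|---|---|---|---|
| 0.3 | 1.40 | 0.91 | 0.65 |
| 0.5 | 1.00 | 0.75 | 0.75 |
| 0.7 | 0.60 | 0.51 | 0.85 |

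**Small-sample cost.** Chance baseline imbalance inflates the ANCOVA variance on average by 1 + 1/(2n − 4): 1.0625 at 10 per group and 1.0278 at 20. ANCOVA then beats both t-tests on variance for rho between √(1 − 1/factor) and 2/factor − 1. That is 0.24 to 0.88 for 20 participants and 0.16 to 0.95 for 40.

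**Power for 10 points, SD 15, two-sided 5%.** Noncentral t with 2n − 2 df for the t-tests; for ANCOVA 2n − 3 df, averaged over chance baseline imbalance.

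| n per group | rho | one-month | change | ANCOVA |
|---|---|---|---|---|
| 20 | 0 | 53.8% | 30.6% | 52.7% |
| 20 | 0.3 | 53.8% | 41.2% | 56.5% |
| 20 | 0.5 | 53.8% | 53.8% | 64.8% |
| 20 | 0.7 | 53.8% | 75.6% | 80.9% |
| 10 | 0 | 29.2% | 17.0% | 27.8% |
| 10 | 0.3 | 29.2% | 22.2% | 30.0% |
| 10 | 0.5 | 29.2% | 29.2% | 35.2% |
| 10 | 0.7 | 29.2% | 44.5% | 48.2% |

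At 20 per group the mean 95% CI half-width is 9.5 points for one-month scores; 11.3, 9.5 and 7.4 for change at rho 0.3, 0.5 and 0.7; and 9.2, 8.4 and 6.9 for ANCOVA. At 10 per group every method exceeds 10 points up to rho 0.7.

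**Other SDs** (20 per group, rho 0.5, one-month against ANCOVA): 63% against 74% at SD 13.4; 44% against 54% at SD 17; 34% against 42% at SD 20.

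**Unequal SDs.** With k = SD(follow-up)/SD(baseline), ANCOVA variance relative to change is (1 − rho²)/(1 + 1/k² − 2rho/k). At rho 0.3, 0.5 and 0.7 this is 0.46, 0.52 and 0.56 for k = 0.75, and 0.78, 0.89 and 0.98 for k = 1.25. In the second case, after the small-sample cost, change is marginally better for rho of about 0.60 to 0.91 (20 participants) or 0.68 to 0.88 (40). At rho 0.7 the cost of ANCOVA is 0.4 power points at 20 per group (81.3% against 80.9%) and 1.7 at 10 per group (49.9% against 48.2%).

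**Main-trial size per group at SD 15** (35.32 × variance factor, rounded up), at rho 0.3, 0.5 and 0.7: 36 throughout for one-month scores; 50, 36 and 22 for change; 33, 27 and 19 for ANCOVA. An observed rho of 0.5 has a 95% CI (Fisher z) of 0.07 to 0.77 with 20 participants and 0.22 to 0.70 with 40. The ANCOVA size therefore ranges over 15 to 36 or 18 to 34 per group.

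**The case against.** The best case against has four parts.

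- **This is a pilot.** Study Design calls feasibility the main objective, and on that view the power of a between-group test is not the criterion. That is fair, but Objectives makes the clinical effect the main aim, and the plan sets a significance level and a between-group test. Planning the main trial needs the right SD in either case.
- **The gain may be small.** At 10 per group and rho 0.3, ANCOVA adds 0.8 power points over one-month scores. Nothing in the documents shows that rho is moderate, and the population mixes traumatic and degenerative injuries, with and without surgery. This stands as a limit on size.
- **Dropout is ignored.** With an illustrative 20% loss (16 or 32 analysed), the range in which ANCOVA beats both tests narrows to rho of about 0.28 to 0.85 or 0.19 to 0.93. Power falls for every method, but the direction holds.
- **The planning quantities are recoverable.** The plan says "Descriptive data will be presented as a mean and standard deviation for continuous variables". If SDs are reported at both visits, rho = (sB² + sF² − sD²)/(2·sB·sF), where sB and sF are the baseline and follow-up SDs and sD, the SD of change, comes from the paired CI. This is correct, so the pilot is not blocked; direct reporting is simply clearer.

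**Conclusion.** The concern holds, as an improvement the sponsor should make rather than the correction of an invalid test. The omission is certain: the test is unadjusted, its quantity is not named, and valid baseline covariates exist. The size of the benefit is illustrative, because it rests on assumed values of SD, rho and the SD ratio, and on equal groups without loss. At rho 0.5 with equal SDs, the large-sample variance falls by 25% on either reading, worth about 11 power points at 20 per group and 6 at 10 per group. The gain vanishes against one-month scores when rho is near 0, and against change when the baseline slope is near 1. ANCOVA does not make 10 per group adequate for detecting 10 points.

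**What to change.** Replace the between-group t-test with a linear model of the one-month score on group and the baseline score of the same measure, separately for DASH and Constant-Murley. Report the adjusted difference with its 95% CI.

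The plan says that "the normality of the data distribution will be assessed by the Shapiro-Wilk test" and gives the t-test for normally distributed data. The adjusted model should be reported whatever that test shows, with a residual check. A bootstrap CI or permutation P value can serve as an optional sensitivity analysis.

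For the main trial, report the follow-up SD, the residual SD and the baseline/follow-up correlation, each with a CI, and size that trial over the CI range of the correlation rather than at its point estimate.

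If the t-test is kept, the minimum change is to state whether it compares one-month scores or changes from baseline.

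The cost is analysis wording. The data are already to be collected, and the model is a standard procedure in SPSS, the package the plan names. It uses one degree of freedom: about 1 to 1.5 power points against one-month scores at rho 0, and up to about 2 against change scores when the baseline slope is near 1.

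### The randomised DASH comparison is planned only as an unadjusted, normality-conditional t-test, with no prespecified between-group estimate or 95% CI and no use of baseline DASH as a covariate

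*Combined protocol and SAP*

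**What the plan says.** The Objectives section gives a clinical aim: "The main aim of the study was to evaluate the effect on clinical variables of monitoring exercises". Patients are randomised to supervised exercise or to eFisioTrack, "or in a separate room without therapist supervision (experimental group"). DASH is the primary outcome, scored 0 to 100 with higher meaning worse, and "The baseline measures will be collected before randomization".

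The Statistical Analysis section then plans three things that bear on the comparison:

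- Summaries: "Descriptive data will be presented as a mean and standard deviation for continuous variables". It does not say whether these are by group.
- Between groups: "To compare differences between groups in the studied variables, the Student's t-test will be used for normally distributed data". Normality is judged by Shapiro-Wilk and significance at P < 0.05. The section does not say whether the test uses one-month scores or change from baseline, and it names no method if normality is rejected.
- Within groups: "For each group, a paired ttest will be used to compare baseline and follow-up scores, and the 95% confidence interval (CI) will be calculated". That sentence closes by tying the interval to mean differences.

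The only other 95% confidence interval in that section is an assumption of the sample-size calculation. On how to read a difference, Outcome Measures says: "Differences in scores are considered clinically relevant (minimum clinically important difference or MCID) when they are above 10 points". Two sizes are given. Study Design says: "That is why the sample size could be between 20 and 40 participants". Statistical Analysis gives a theoretical 36 per group.

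**The concern.** Randomisation protects the contrast between arms, yet the plan attaches its statement of precision to change inside each arm. Improvement in both arms over a month says nothing about the gap between them. A P value for the gap does not show which sizes of gap remain compatible with the data. With 20 to 40 patients, a non-significant result could mean arms that are close or a sample too small to tell, and only an interval shows which.

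Two further losses follow from the wording. Baseline DASH is already in hand, but no adjustment is planned, so precision is given away. And because the test is stated only for normal data, a Shapiro-Wilk rejection leaves the primary outcome with no named between-group analysis.

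This concerns the clinical aim. It does not touch the SD, recruitment, dropout and compliance estimates that Study Design lists as the pilot's feasibility outputs.

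**Working it through.** **1. The plan's own figure.** Inputs from Statistical Analysis: difference 10 points, power 80%, 95% confidence (two-sided 0.05 assumed). The SD is not stated. With n per group = 2(z₀.₉₇₅ + z₀.₈₀)² SD² / Δ², an SD of 15 gives 2 × (1.960 + 0.842)² × 225 / 100 = 35.3, rounded up to 36. Solving back from 36 gives SD 15.1. The figure cannot be confirmed, because the 20% sampling error is undefined: read as dropout, it implies an SD of about 13.5; read as an SD of 20, it would require 63 per group. SD 15 is therefore used as an illustration and SD 10 to 25 as the range, with 1:1 allocation assumed.

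**2. Unadjusted interval for one-month scores.** Half-width = t(0.975, 2n−2) × SD × √(2/n). At SD 15:

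- 10 per arm: 2.101 × 15 × √0.2 = 14.1
- 20 per arm: 2.024 × 15 × √0.1 = 9.6
- 36 per arm: 1.994 × 15 × √(2/36) = 7.05

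Over SD 10 to 25 these run 9.4–23.5, 6.4–16.0 and 4.7–11.8 points.

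**3. Interval adjusted for baseline DASH.** With baseline correlation r, the ANCOVA half-width is close to t(0.975, 2n−3) × SD × √(1−r²) × √(2/n) × √(1 + 1/(2n−4)). For 20 per arm and r = 0.5: 2.026 × 15 × 0.866 × 0.316 × 1.014 = 8.4. Simulated means (40,000 trials per setting) agree. The correlation is an assumption.

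| Per arm | Unadjusted | r = 0.3 | r = 0.5 | r = 0.7 |
|---|---|---|---|---|
| 10 | 14.1 | 13.7 | 12.5 | 10.3 |
| 20 | 9.6 | 9.2 | 8.4 | 6.9 |
| 36 | 7.0 | 6.8 | 6.1 | 5.1 |

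**4. If the t-test was meant for change scores.** The unadjusted half-width is multiplied by √(2(1−r)), that is 1.18, 1.00 and 0.77 at r = 0.3, 0.5 and 0.7. At 20 per arm this gives 11.4, 9.6 and 7.4, again wider than ANCOVA (9.2, 8.4 and 6.9).

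**5. The normality condition.** If each arm is tested at 0.05, which the section does not specify, truly normal data are rejected in at least one arm with probability 1 − 0.95² = 0.0975. Simulation gave about 9%. In those trials the plan names no comparison.

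**6. Does the adjusted interval need normal data?** In 3,000 simulated trials per setting with normal, gamma and exponential errors, r = 0.5, and 10 or 20 per arm, the ANCOVA t interval covered 0.950 to 0.958. A percentile bootstrap covered 0.908 to 0.935. The t interval can stand without a preliminary test, and a bootstrap would not improve on it.

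**The case against.** The strongest reply is that little is truly lost. If means and SDs are given by group with group sizes, a reader can compute the unadjusted difference and its interval. The interval sentence ends on mean differences and follows a sentence about differences between groups, so it might be stretched to cover both. This is also a pilot, and Study Design names feasibility and SD estimation as its main objective.

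Much of this stands, and it keeps the point minor. It does not remove it. The interval sentence opens by restricting itself to each group and concerns the paired test. A reader cannot recover a baseline-adjusted difference from means and SDs, and reconstruction by readers is not a prespecified analysis.

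Three stronger readings are tempting and should be resisted.

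- A reader might infer that the protocol will treat non-significance as equivalence. It makes no such claim, and the Project Summary calls the results preliminary.
- A reader might say that the MCID is ignored. Outcome Measures gives it as a threshold of clinical relevance, and the sample-size calculation uses a 10-point difference between groups. What is missing is a link from it to a between-group estimate.
- A reader might size the fault by low power. At SD 15 a true 10-point difference gives P ≥ 0.05 in 71% of trials at 10 per arm and 46% at 20. Those figures describe the sample size, and reporting an interval does not in itself change them. At the stated 36 per group, power would be about 80%.

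**Conclusion.** The point holds as a minor weakness of analysis choice. For the primary outcome the plan prespecifies a conditional, unadjusted test and, on the natural reading of the text, no between-group estimate or interval.

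The gain from adjustment depends on a correlation that the documents do not give. At r = 0.3 it is slight (about 14 to 13.7 points at 10 per arm); at r = 0.7 it is substantial (9.6 to 6.9 at 20 per arm). The half-widths assume SD 15 and 1:1 allocation, and scale in proportion to the SD. Which sample size governs, 20 to 40 in total or 36 per group, changes the width but not the conclusion.

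**What to change.** In Statistical Analysis, for DASH, replace the Shapiro-Wilk-conditional t-test as the between-group analysis with wording such as:

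*The arms will be compared by the difference in mean one-month DASH (eFisioTrack minus supervised), adjusted for baseline DASH by ANCOVA, with its two-sided 95% CI, reported whatever the Shapiro-Wilk result. The estimate and interval will be described against the 10-point MCID, which is not a pass/fail margin. Paired tests within groups are descriptive and will not be used to compare the arms.*

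This should replace the t-test for DASH, so that two between-group analyses do not compete. With baseline as a covariate, the estimated difference is the same whether the outcome is the one-month score or the change, which settles the unstated choice. No bootstrap interval is needed.

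The cost is three sentences and one model, with no extra patients or data. The downside is candour about imprecision. With truly equal arms at SD 15, the upper limit falls below 10 points in only 29% of trials at 10 per arm and 54% at 20 unadjusted, and in 30–48% and 56–81% adjusted (r = 0.3 to 0.7). At 36 per arm the unadjusted figure is about 80%. At 20 to 40 patients the clinical comparison will often have to be reported as inconclusive.

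### The 36 per group at 80% power is not tied to this study or to the later trial, lacks an SD and a defined 20% term, and does not describe a pilot of 20 to 40 participants

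*Combined protocol and SAP*

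**What the plan says.** Two sections give a sample size, and neither refers to the other.

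- **Study Design, Regarding sample size.** The purpose is stated as feasibility: "The main objective of this study is to know whether a clinical trial will be feasible". The study is also to "have an estimate of standard deviation, which will be used in the sample size calculation for the large-scale trial", and to estimate rates of willingness, dropout and compliance. The size follows from this: "That is why the sample size could be between 20 and 40 participants". The text does not say whether that is a total or per group.
- **Statistical Analysis.** After the description of the tests comes "The theoretical sample size based on a 10-point difference (10%) in the DASH between the two studied groups", with a 95% confidence level and 80% power, ending "20% sampling error, resulted in 36 patients in each group". No SD, source or sidedness is given, and the 20% is not explained anywhere. The next paragraph sets this study's software and its 0.05 significance level.

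Three other places bear on the point.

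- The Objectives section begins "The main aim of the study was to evaluate the effect on clinical variables", so it puts clinical effect first where the sample-size paragraph puts feasibility first.
- The Outcome Measures section sets clinical relevance at more than 10 DASH points.
- In the Statistical Analysis section, the between-group comparison ("To compare differences between groups in the studied variables") names a t-test for normally distributed data. A confidence interval appears only in the sentence on within-group paired tests ("to compare baseline and follow-up scores, and the 95% confidence interval (CI) will be calculated for the mean differences").

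**The concern.** The power statement stands among this study's own tests and threshold and speaks of the two studied groups. A reader can therefore take 80% power for 10 DASH points as applying to this study. Read as a total, 20 to 40 is only 28% to 56% of the 72 patients that 36 per group implies (20/72 and 40/72).

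The experimental group exercises without a therapist in the room. A non-significant t-test, reported next to an 80% power statement, could be taken to show that supervision makes no difference. The planned size may not support that, and no between-group interval is explicitly planned that would show the imprecision.

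There is also a question of order. The SD for the large-scale calculation is to come from this study, yet a figure that needs an SD is already reported. Any SD behind the 36 can only be provisional, and it is not shown.

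**Working it through.** **Inputs from the documents:** difference 10 points; significance level 0.05; power 80%; 36 per group; 20 to 40 participants; Student's t-test.

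**Assumptions:** two-sided test (sidedness is not stated); equal groups; 20 to 40 read as a total, so n = 10 to 20 per group; no dropout unless stated.

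**1. Can the 36 be reproduced?** Not from the stated inputs, because the SD is missing. Using the normal formula n = 2(1.960 + 0.842)² × SD²/10² per group:

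- SD 15 gives 2 × 7.849 × 225/100 = 35.3, so 36. The figure is attainable.
- SDs for which 36 is the smallest sufficient n are about 14.9 to 15.1 (normal formula) or 14.7 to 14.9 (t-test).
- Taking the 20% as an SD of 20 points gives 63 per group, which does not match.
- Taking the 20% as type II error only restates the 80% power.
- Taking the 20% as dropout, inflation by 1/(1 − 0.2) gives 35 or 37 for SDs of about 13.1 to 13.6 but never exactly 36. Multiplying by 1.2 gives 36 for SDs of about 13.6 to 13.8.

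**2. Reading A: all 36 per group are analysed.** Power is that of a two-sample t-test with 2n − 2 degrees of freedom and noncentrality 10/(SD × √(2/n)). Setting it to 80% at n = 36 gives SD = 14.93. The difference detectable with 80% power is 10 × d(n)/d(36), where d is the standardised detectable difference. On this reading the SD cancels.

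**3. Reading B: the 20% is a dropout allowance.** Then 36 × 0.8 = 28.8, or about 29 analysed per group. Setting power to 80% at n = 29 gives SD of about 13.4.

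| Reading | Patients in total | Power for 10 points | Detectable with 80% power |
|---|---|---|---|
| A, SD 14.93 | 20 | 29% | 19.8 points |
| A, SD 14.93 | 40 | 54% | 13.6 points |
| B, SD 13.4, no pilot dropout | 20 | 35% | 17.7 points |
| B, SD 13.4, no pilot dropout | 40 | 64% | 12.1 points |
| B, pilot also loses 20% (8 per group) | 20 | 29% | not tabulated |
| B, pilot also loses 20% (16 per group) | 40 | 54% | not tabulated |

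**4. Other variants of reading A.**

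- One-sided 5%: SD 16.9, power 36% and 58%, detectable differences 19.5 and 13.5 points.
- If 20 to 40 is per group: power 54% to 84% (two-sided), and 36 lies inside the planned range.

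**5. Precision of the between-group difference.** The 95% CI half-width is t(0.975, 2n − 2) × SD × √(2/n). With an assumed SD of 15 and no dropout:

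- 20 patients: 2.101 × 15 × √(2/10) = 14.1 points.
- 40 patients: 2.024 × 15 × √(2/20) = 9.6 points.

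**The case against.** The best defence is that the documents already say what governs this study. The title and design call it a pilot feasibility study. The paragraph on sample size gives 20 to 40 with a feasibility reason, and the 36 is labelled theoretical. A pilot need not be powered for a clinical difference, and no sentence claims 80% power at 20 to 40. Most of this stands. A benchmark for the later trial is the likelier reading, so it would be too strong to say that nothing indicates this study's size.

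The defence does not remove the ambiguity. The figure is never assigned to the later trial. It refers to the two studied groups and sits between this study's tests and its significance level, and the Objectives section puts clinical effect first. Even as a benchmark it cannot be checked.

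A second objection is that the power figures depend on what the 20% means. That is also right. A reader might infer that 29% and 54% follow from the 36 and 80% pair whatever SD was used, but this holds only if all 36 per group are analysed. Under a dropout reading the figures are higher, though still below 80% for 20 to 40 in total.

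Finally, the between-group interval is a reporting point and would not by itself link the two sizes. It is included because it costs almost nothing and guards against the misreading described above.

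**Conclusion.** The point holds as an ambiguity and an incomplete calculation. The two sizes are not linked, the SD and its source are absent, and the 20% is undefined. These omissions are certain from the text.

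The size of the consequence is conditional. For 20 to 40 participants in total and a two-sided 5% test, power for 10 points runs from about 29% to 54% (all 36 analysed) or 35% to 64% (20% as dropout, none lost in the pilot). The differences detectable with 80% power run from 19.8 down to 13.6 points, or from 17.7 down to 12.1. All of these exceed the 10-point threshold. If 20 to 40 is per group, the first reading gives 54% to 84%, and the conclusion about power would no longer apply across the whole range.

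A reader might go further in two ways that the documents do not support. One is that 36 is miscalculated: an SD near 15 yields it, so it is uncheckable and not shown to be wrong. The other is that this study must recruit 72: the feasibility rationale justifies a smaller pilot, and nothing states that 36 per group is its target.

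This should be fixed before results are interpreted.

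**What to change.** 1. State one N, or one range, for this study, and say whether it is a total or per group.
2. State which study the 36 per group at 80% power applies to. Give the assumed SD, its source and the sidedness, and define or delete the 20% term. Alternatively, remove the figure.
3. If this study enrols 20 to 40 in total, do not attach 80% power for 10 DASH points to it. Restate the power, or say that the size rests on feasibility.
4. Report the between-group DASH difference with its 95% CI beside the t-test, so that a non-significant result is not read as no difference.

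If the size stays at 20 to 40, the cost is wording in two paragraphs and one extra interval, and the stated power becomes less favourable. Only the authors can say which study the 36 belongs to. If they declare it to be this study's target, the planned enrolment in the Study Design section would have to be reconciled with 72 patients, which is more than a wording change.
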